codes), Eskenazi clinic(s) of care Health care utilization retrospective review: • The presence of outpatient sick visits within the Eskenazi system clinic for any complaint • The presence of outpatient sick visits within the Eskenazi system clinic with an associated GI billing code • The presence of visits to statewide providers, including inpatient hospital stays, outpatient clinic visits, and emergency room visits. • The occurrence of any GI-related testing and procedures – specifically radiologic, laboratory testing, endoscopy, and surgical procedures related to GI diagnoses • The use of any medications prescribed to treat Rome IV diagnoses – specifically acid-suppressants, antispasmodics, antidepressants, stool softeners and laxatives, and pro-motility agents.

q23340

Would identification of subjects and/or their responses reasonably place them at risk for any of the following (check any that apply):

None

B-Lay Summary Research Design

q22122

Describe the purpose of this study in lay terms, including research question(s) and hypothesis.

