Systematic Pediatric Assessment of Rome Criteria (SPARC)

Principal Investigator: [name] MD

IRB Protocol # 1811325201

NCT04773158

April 1, 2019

**Sample Size and Power Estimates.** We calculated our sample size using the binary primary outcome (whether there was resolution of symptoms of a FGID by Rome IV criteria in children and adolescents or whether parental reassurance was achieved for infants). We wish to detect a 15% difference between the control and intervention clinics in the rate of the primary outcome. Since each FGID has a different estimated background rate of improvement without intervention, we estimated an overall weighted average improvement rate. We also took into consideration of differences of prevalence of different FGID diagnosis. Therefore, based on the data presented in Table 3, we estimated an overall improvement rate of 30% for the control clinics. Though we do not anticipate much variability in this rate at our six study clinics, we will use six different rates in a wide range, 15%, 20%, 25%, 30%, 35% and 40%, at baseline in order to estimate intra-clinic correlation. This translates to an intra-class correlation coefficient 0.007. However, for a conservative estimation of sample size, we will use intra-class correlation 0.014, two times the intra-class correlation we estimated.

Table 3. Data Utilized for Sample Size Calculations				
FGID Diagnosis	Estimated Baseline Improvement in 3 months	Prevalence	Unique CHICA patients/yr in age group	Minimum Time Required
Infant regurgitation (0-12m)	25%	10%	3172	10 months
Infant dyschezia (0-9m)	25%	5%	2640	26 months
Infant colic (0-5m)	48% 	10%	1584	26 months
Cyclic vomiting syndrome (3m-18y)	70% 	5%	22544	4 months
Functional nausea/vomiting (8-18y)	50%	5%	9702	8 months
Functional dyspepsia (8-18y)	25%	10%	9702	4 months
Irritable bowel syndrome (8-18y)	37.5% 	15% 	9702	4 months
Abdominal migraine (8-18y)	20%	2% 	9702	16 months
Functional abdominal pain - NOS	20%	15%	9702	4 months
Functional constipation (0-18y)	20%	20%	23336	3 months

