Using a chi-square test and setting alpha at 0.05, the probability of detecting a statistically significant difference in the proportion of children with symptoms of any FGID with improvement in the primary outcome at 3 months from baseline between the intervention and the control group is 90%, with an effective sample size of 163 per group. Hence, the total effective sample size (n\*) is 326.

The unit of randomization is the clinic, but the unit of analysis is the individual patient. Since patients are nested within practice, responses from the patients within practice are likely to be

correlated. This intra-cluster correlation must be taken into account in the calculation of sample size and in the analyses. We computed the number of patients per clinic,  $m$ , required for the study, using the following equation:

$$m = \frac{1 - \rho}{\frac{k}{n^*} - \rho}$$

where  $\rho$  = intra-practice correlation  
 $k$  = number of clinics  
 $mk$  = total sample size  
 $n^*$  = total effective sample size =  $mk/DE$   
and  $DE$  = design effect =  $1 + \rho(m-1)$

Using 6 clinics and assuming intra-class correlation of 0.014, we need to recruit 224 families with a child between 0 and 18 per clinic. We anticipate that drop-out is not a major problem and unlikely to be more than 10% for the primary outcome. We will account for this factor by oversampling patients by 10%. According to the data presented in Table 3 and with an assumption that for each category of FGID diagnosis 50% of the patients will be in the control clinics and other 50% will be in intervention clinics, there will be about 5,500 patients/year/group with a FGID diagnosis. If we assume that only 66% of the parents will respond to the phone call at 3-month post baseline, we will have 3,630 patients/year/group. Therefore, the number of patients from which we are able to recruit is not a factor at all. We can have more than 90% power even to detect a 5% absolute difference with all available patients in one year.

**Data Analysis.** Baseline clinical and demographic data will be compared between the intervention and the control groups. Categorical variables will be examined using chi-square tests and continuous measures with Student's t-tests. The statistical analysis of the data will be performed using the SAS.

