**Primary Outcome Analysis:** The primary outcome is whether there was resolution of symptoms of a FGID by Rome IV criteria in children and adolescents or whether parental reassurance was achieved for infants. For this dichotomous outcome, we will use a non-linear mixed-effects model and will adjust for potential confounders (fixed effects) and clinic effects (random effects). To be specific, if  $Y_{ik}$  is a binary variable indicating whether the  $k^{\text{th}}$  patient in the  $i^{\text{th}}$  clinic was reported a resolution of FGID symptom, we have

$$\text{logit}(Y_{ik} = 1) = \alpha_i + \mathbf{X}_{ik}\beta, \text{ where } \alpha_i \sim N(0, \sigma^2).$$

The random component  $\alpha_i$  correlates outcomes of patients cared by the same clinic. Physicians would not be considered as a nesting factor since the same patients at different visits may not be seen by the same physician. The vector  $\mathbf{X}_{ik}$  represents fixed covariates and  $\beta$  represents the corresponding coefficients. The fixed covariates will include critical covariates such as treatment group, gender, and other patient and clinic level characteristics. We will also examine potential interaction terms among the covariates, particularly interactions between treatment arm and other covariates. If there is a significant treatment difference, we will report the 95% confidence interval of the treatment difference after adjusting for all confounding factors. The model will be fitted by the SAS procedure NL MIXED.

**Secondary Outcome Analyses:** The additional time points of 1, 6, and 12 months will be modeled identically to the primary outcome analysis. Furthermore, we will have a number of secondary outcomes which are count data aggregated within the 12 months after initial Rome IV

diagnosis. We will use Poisson regression to model these count data. To adjust for the possible differences between the intervention and control groups, we will use an approach similar to the analyses of primary outcomes and again clinic will be considered as a cluster factor to take into consideration the correlation in count data within each clinic. Family and provider satisfaction scores will be analyzed using Student's t-test, as well as a linear mixed-effects model as with other outcomes.

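### The Poisson analysis of 12-month utilisation counts tests a clinic-level treatment effect on six clinics with no small-sample reference, and has no patient-level dispersion term for the planned interactions

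*SAP*

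**What the plan says.** SAP, Secondary Outcome Analyses: for the outcomes that are counts over the 12 months after the initial diagnosis, "We will use Poisson regression to model these count data". The SAP says the adjustment will resemble that of the primary analysis and that clinic will again be a cluster factor. The primary model has a normal random intercept per clinic, and its covariates include treatment group and treatment-by-covariate interactions.

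SAP, Sample Size and Power Estimates: the clinic is the unit of randomisation. "Using 6 clinics and assuming intra-class correlation of 0.014", the SAP concludes that "we need to recruit 224 families with a child between 0 and 18 per clinic".

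For the counts, the SAP names no negative binomial model, scale parameter, patient-level random effect, robust variance, degrees of freedom or small-sample correction. It also states no event rate or dispersion.

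Protocol, section A, q725, lists the utilisation data points, for example "The presence of outpatient sick visits within the Eskenazi system clinic for any complaint". The same style of entry recurs in section K (q23650) and in the Protocol Determinations (item 9010). Section B (q22122) makes reduced utilisation part of the trial's hypothesis, as secondary outcomes.

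**The concern.** Treatment varies only between clinics, so the evidence on it is in effect six clinic averages, three per arm if allocation is balanced. After two arm means are fitted, 4 degrees of freedom remain for the variance between clinics. A maximum-likelihood fit tends to underestimate that variance, and a normal reference then treats it as known. Both push the false-positive rate up.

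The second gap is at patient level. Poisson fixes the variance at the mean within a clinic. If visit, test or prescription counts vary more than that, comparisons made within clinics, such as treatment-by-sex interactions, have standard errors that are too small.

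At stake is a false claim that the module reduces health-care use overall, or reduces it in a subgroup.

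**Working it through.** **The plan's own figure.** With ρ = 0.014, k = 6 clinics and n* = 326, m = (1 − ρ)/(k/n* − ρ) = 0.986/(0.018405 − 0.014) = 223.8, so 224 per clinic. This reproduces.

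**Inputs from the documents.** Six clinics; 224 children per clinic; ICC 0.014; alpha 0.05 (the power section says "setting alpha at 0.05", taken as two-sided and applied to the counts too).

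**Assumed inputs.** Three clinics per arm; mean μ = 2 events per child; negative binomial dispersion d = 0, 1 or 2, so variance = μ + dμ² = 2, 6 or 10 and variance/mean = 1, 3 or 5; clinic SD σ on the log scale from 0 to 0.20; maximum-likelihood fitting of a normal clinic intercept.

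**Link to the planning ICC.** At μ = 2 and d = 1, σ = 0.146 gives between-clinic variance (2 × 0.146)² = 0.0853 and ICC = 0.0853/(0.0853 + 6) = 0.014. The SAP derives 0.014 for the binary primary outcome, so its use for counts is an analogy.

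**Few-clinic effect, analytically.** Maximum likelihood divides the between-clinic sum of squares by 6 rather than 4, so the Wald statistic is √(6/4) times a t statistic on 4 df. The actual rejection rate is P(|t₄| > c√(4/6)):
- normal reference, c = 1.960: P(|t₄| > 1.600) = 18.5%
- t on 5 df, c = 2.571: P(|t₄| > 2.099) = 10.4%
- t on 4 df, c = 2.776: P(|t₄| > 2.267) = 8.6%

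A 4-df critical value is therefore not enough unless the variance is also estimated on 4 df.

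**Treatment test under the null, simulated.** Poisson with a clinic intercept, normal reference, 1,000 runs per cell:

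| Clinic SD | d = 0 | d = 1 | d = 2 |
|---|---|---|---|
| 0 | 4.2% | 12.7% | 16.8% |
| 0.05 | 12.3% | 16.5% | 17.9% |
| 0.146 | 19.1% | 19.1% | 17.2% |
| 0.20 | 19.8% | 19.3% | 18.1% |

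With t on 5 df, the row for SD 0.146 becomes 10.7%, 10.5% and 9.8%.

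**Why overdispersion drops out at SD 0.146.** The variance of a clinic's log mean is about σ² + (μ + dμ²)/(mμ²). At d = 1 this is 0.0213 + 6/(224 × 4) = 0.0213 + 0.0067. Poisson accounts for 2/(224 × 4) = 0.0022 of the second term. The remaining 0.0045 goes into the estimated clinic variance. Only when σ is near zero does that excess dominate.

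**Negative binomial with the same clinic intercept.** 600 paired runs, normal reference, Poisson → negative binomial:
- SD 0.146: 18.7% → 16.7% (d = 1); 21.5% → 17.2% (d = 2)
- SD 0.10, d = 1: 19.7% → 14.3%
- SD 0.05, d = 1: 15.0% → 7.5%
- SD 0: 14.3% → 6.7% (d = 1); 18.8% → 6.5% (d = 2)

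**Clinic-level t-test.** A t-test on clinic log means with 4 df rejected 4.1% to 6.7% in every cell. Monte Carlo standard errors are about 0.7 to 1.7 points throughout.

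**Within-clinic interactions.** If the true variance is φ times the Poisson variance, rejection is P(|Z| > 1.96/√φ). For φ = 2, 3 and 5 the cut-offs are 1.386, 1.132 and 0.877, giving 17%, 26% and 38%. A simulation of a null treatment-by-sex interaction (1,000 runs, SD 0.146, clinics fitted as fixed effects) gave 5.8%, 16.4%, 28.3% and 38.0% for φ = 1, 2, 3 and 5.

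**The case against.** The strongest reply is that the SAP does include clinic as a cluster factor. For a treatment that varies only between clinics, the clinic effect absorbs patient-level excess variance. This stands, and it rules out a tempting inference: that missing overdispersion is what breaks the treatment test, and that negative binomial would repair it. At SD 0.146 the test over-rejects equally with no overdispersion, and the change of model gains only about 2 to 4 points.

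It may also be said that 224 per clinic is the wrong size here. That number is the recruitment target for the primary outcome, whereas utilisation comes from record queries (Protocol, section B, q22123). The SAP expects about 5,500 patients with a diagnosis per group per year, or 5,500/3 ≈ 1,830 per clinic. This also stands. A normal approximation at that size (d = 1) gives Poisson 18.3% against negative binomial 16.3% at SD 0.05, and 18.5% for both at SD 0.146. More patients leave the few-clinic problem intact and make dispersion matter less for the treatment test. They do not help the interactions, where φ does not depend on sample size.

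In the other direction, the SAP expects little variation between clinics in the primary outcome, which gives some weight to the rows near SD 0. There overdispersion does matter.

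Finally, a reader might infer that presence fields cannot feed a count model at all. The documents do not support that. The form lists categories of data, section B (q22122) gives repeat visits as an example of utilisation, and the record queries could return dates. It is a mismatch of wording between protocol and SAP.

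**Conclusion.** The point holds, with the small number of clinics as the main cause and dispersion second. At clinic variation near the SAP's planning value, the planned treatment test on the counts would reject a true null at roughly two to four times the nominal 5%, depending on whether a t or normal reference is used. The only cell near nominal with a normal reference has neither clinic variation nor overdispersion.

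Missing dispersion matters in two settings: when clinics are almost identical (about 13 to 19% for Poisson against about 7% for negative binomial, at SD 0), and in treatment-by-covariate interactions at any level of clinic variation.

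These sizes rest on the assumed mean and dispersion, three clinics per arm, maximum-likelihood fitting, and reading the cluster factor as a random intercept. The finding that overdispersion adds nothing at SD 0.146 is for a fixed clinic SD; with d = 0, an ICC of 0.014 would correspond to an SD of about 0.084, where the table implies between 12% and 19%. Rejection rates for Poisson with no clinic term are higher still, but that is not the planned model. The outcomes are secondary, so this should be corrected but does not threaten the primary analysis of the trial.

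**What to change.** 1. **Lead item.** State that the treatment effect on each count will be tested against 4 between-clinic degrees of freedom with REML-type variance estimation, or by a t-test on clinic-level log means. Changing the reference to t on 4 df while keeping the maximum-likelihood variance is not sufficient (8.6%).
2. **Second item.** Replace Poisson with negative binomial regression, keeping the clinic effect, so that tests of patient covariates and treatment-by-covariate interactions allow for variance above the mean. This was not simulated for the interactions; it follows from the variance model.
3. **Protocol wording.** In section A (q725), section K (q23650) and item 9010, record the number and dates of visits, tests and prescriptions, to match the counts in the SAP.

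The cost is wider intervals and less power on the secondary outcomes (the two-sided critical value rises from 1.96 to 2.78), one extra parameter, and wording changes in both documents. No further patients are needed.

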Missing Data Analysis: We anticipate a low rate of missing data for the primary outcome since our CHICA system showed only 1.3% error rate due to omission of a data field. However, we anticipate a possible dropout rate of 10% for which we have adjusted the sample size. It is very unlikely that the dropout mechanism will depend on the unobserved outcome. Even if MNAR is true for certain subjects; given the low percentage of missing values, we think the bias induced is negligible. Under circumstances where compromise of power due to missing values is of concern, we will use a multiple imputation procedure to make use of all relevant observed data under the assumption that the data are Missing At Random (MAR). The SAS procedure MI and MIANALYZE will be used to implement the procedure.

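### The SAP names single-level PROC MI for missing primary outcomes and gives clinic no stated role, so the treatment effect's standard error can be mis-sized in either direction

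*SAP*

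**What the plan says.** The SAP's sample-size section states that clinics are randomised and children analysed, and says of the resulting correlation: "This intra-cluster correlation must be taken into account in the calculation of sample size and in the analyses". The Primary Outcome Analysis follows this with a logistic mixed model that has a normally distributed random intercept for clinic, fitted in NLMIXED.

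The Missing Data Analysis expects about 10% dropout. If lost power becomes a worry, it turns to multiple imputation under MAR, drawing on whatever relevant data were observed: "The SAS procedure MI and MIANALYZE will be used to implement the procedure". No imputation model is given. Neither clinic nor treatment arm is named there, and neither is excluded.

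Two response figures appear. The allowance for dropout in the primary outcome is 10%, in both the sample-size and missing-data sections. The sample-size section also sizes the pool of available patients with a lower figure: "If we assume that only 66% of the parents will respond to the phone call at 3-month post baseline".

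**The concern.** With three clinics per arm, variation between clinics is a large part of the uncertainty in the treatment effect. A single-level imputation model without clinic draws each missing outcome around the arm average, not around the rate in the child's own clinic. The completed clinic rates are pulled together, and the mixed model then reads that artificial agreement as low clinic variance. The arm difference is no better known, but its interval narrows.

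The SAP would impute in order to protect power, so a spurious gain in precision would appear in just the situation where imputation is invoked. PROC MI does allow clinic as a class variable, but that route errs the other way: clinic rates estimated with noise add spread between clinics, and the combining rules count that noise a second time.

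**Working it through.** **Inputs from the SAP.** Six clinics; total effective sample size 326; ICC 0.014 ("for a conservative estimation of sample size, we will use intra-class correlation 0.014") and its unadjusted estimate, 0.007; dropout 10%; phone response 66%, so non-response 100% - 66% = 34%.

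**Assumptions.** Three equal clinics per arm; outcomes missing completely at random; arm included in the imputation model (the SAP does not say); analysis on clinic proportions, total variance scaled to 1; many imputations.

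**The plan's own cluster size.** m = (1 - 0.014) / (6/326 - 0.014) = 0.986 / (0.018405 - 0.014) = 223.8, so 224 per clinic reproduces. Oversampling by 10% gives 224 x 1.1 = 246.4, or 247. Whether 163 per group delivers the stated power is a separate question. It does not affect the SE ratio at a given cluster size.

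**A third ICC, derived and not stated.** The SAP's six clinic rates (15% to 40% in steps of 5) have mean 0.275 and variance 0.0073. Dividing by 0.275 x 0.725 = 0.1994 gives 0.037. The SAP's 0.007 matches the raw variance before that division.

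**Formulas.** With response fraction r, N children per clinic and ICC ρ, per clinic:

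- True variance: V = ρ + (1-ρ)/(rN)
- Clinic omitted, within-imputation: W = r²ρ + r(1-ρ)/N + (1-r)/N
- Clinic omitted, between-imputation: B = (1-r)²/(rN) + (1-r)/N
- SE ratio = √[(W+B)/V]
- Clinic as class variable: added noise E = (1-r)²(1-ρ)/(rN) + (1-r)(1-ρ)/N; SE ratio = √[(V+2E)/V]

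**Worked case: r = 0.66, N = 224, ρ = 0.014.**

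- V = 0.014 + 0.986/147.84 = 0.02067
- W = 0.00610 + 0.00291 + 0.00152 = 0.01052
- B = 0.00078 + 0.00152 = 0.00230
- Clinic omitted: √(0.01282/0.02067) = 0.788, so the SE is 21.2% too small
- Class variable: E = 0.00227; √(0.02520/0.02067) = 1.104, so the SE is 10.4% too large

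**Results at 224 per clinic.**

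| Missing | ICC | Clinic omitted: SE too small by | Clinic as class variable: SE too large by |
|---|---|---|---|
| 10% | 0.007 | 5.7% | 4.0% |
| 10% | 0.014 | 7.3% | 2.6% |
| 10% | 0.037 | 8.7% | 1.1% |
| 34% | 0.007 | 15.5% | 15.5% |
| 34% | 0.014 | 21.2% | 10.4% |
| 34% | 0.037 | 27.6% | 5.0% |

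**Simulation.** With six beta-binomial clinics, 247 per clinic, 10 imputations and 3,000 runs at 34% missing, the SE with clinic omitted was 22.5% (ICC 0.014) and 29.9% (ICC 0.037) too small. The formula at 247 gives 22.0% and 28.1%. With clinic as a class variable the SE was 10.9% and 3.6% too large. Null rejection with clinic omitted, on a t distribution with 4 degrees of freedom, was 6.1% and 10.2%, against 4.6% and 4.7% from the observed data alone.

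**Sensitivity to clinic size.** The Protocol's answer on research interactions foresees at most 600 survey participants, about 100 per clinic if spread evenly. At N = 100 with clinic omitted, the shortfall is about 14.5% (ICC 0.014) and 22% (ICC 0.037) at 34% missing, and 5.4% and 7.6% at 10%.

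**The case against.** The strongest reply is that the SAP never leaves clinic out. It promises to use the relevant observed data, clinic is observed and is the unit of randomisation, and entering it as a class variable removes the shrinkage. A reader might infer that the plan commits to an SE that is 21-28% too small. The documents do not support that, for four reasons:

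- Omission of clinic is possible but not stated.
- 34% is not the plan's missing-data rate. It is the complement of a response rate used only to show that enough patients exist. The planned rate is 10%, where the error is 7-9%.
- The upper end needs an ICC of 0.037, which the SAP does not state. At its 0.007 the figure at 34% missing is about 16%.
- Imputation is conditional, and the primary analysis is already the random-intercept model.

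All of this stands as a limit on size. It does not remove the point. Adding clinic to PROC MI replaces an SE that is too small with one that is too large, so at substantial missingness neither route gives the right SE. The SAP's 66% refers to the same 3-month call at which the primary outcome is collected, and it is not reconciled with 10%. Because the oversampling already covers a 10% loss, a concern about power would most plausibly arise above that level, where the error grows.

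A further caution concerns attribution. In 250 simulated trials analysed with a maximum-likelihood random-intercept logistic model (ICC 0.014, 34% missing), the mean SE fell from 0.219 to 0.184 when clinic was omitted from imputation, a drop of 16% (0.184/0.219 = 0.84). The true spread barely moved (0.256 and 0.254). But 0.219 is itself 14% below 0.256. That part comes from having few clinics, not from imputation.

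**Conclusion.** The concern holds in conditional form. The named procedure cannot represent the clinic effect that the SAP itself requires the analyses to respect, and the SAP does not say how clinic would be handled. If clinic is omitted, the SE is about 7-9% too small at 10% missing (ICC 0.014 to 0.037). At 34% missing it is about 16%, 21% and 28% too small at ICCs of 0.007, 0.014 and 0.037. If clinic is a class variable, the SE is too large: by about 5-10% at 34% missing for ICCs of 0.037 to 0.014 (more at 0.007), and by a few percent or less at 10%.

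These sizes rest on 224 children per clinic, equal clinics, loss completely at random and arm being in the imputation model. With clinic omitted, the shortfall is smaller with fewer children per clinic.

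**What to change.** State in the SAP that the primary analysis fits the planned random-intercept model to all observed 3-month outcomes, under MAR given the model covariates. This needs no imputation of the outcome. Imputing it from the same covariates would add essentially no information about the arm difference.

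That MAR condition is not identical to one that also conditions on children's answers at other time points. If the 1-, 6- and 12-month answers are to be brought in, replace single-level PROC MI with a multilevel imputation that includes treatment arm and a random clinic effect, and write out that model.

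The cost is SAP wording, a little programming if multilevel imputation is used, and possibly a wider reported interval.
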